5.7 Graphs and other data summaries

- The flow of study participants will be displayed in Consolidated Standards of Reporting Trials (CONSORT) diagram.
- 30-day and one-year survival of patients will be presented for both groups using Kaplan-Meier survival curves.
- Investigator self-assessment of blinding by treatment allocation will be presented as number (%).
- Duration of level 2 and 3 critical care stay within 30 days of randomisation for patients admitted to a critical care unit will be presented as mean (SD) and median (IQR).
- Data describing a predefined list of the most common post-operative complications occurring within 30 days of randomisation will be collected for all patients.

The number and percentage of patients experiencing each of the following complications will be presented by (a) treatment allocation; (b) treatment allocation and Clavien-Dindo (CD) grade (I-II vs III-V); and (c) treatment allocation and CPAP delivery method for those in the CPAP group only. These summaries will not be subjected to any statistical testing. These complications are:

Respiratory complications:

- o Pneumonia
- o Pleural effusion
- o Pneumothorax
- o Bronchospasm
- Aspiration pneumonitis
- Acute Respiratory Distress Syndrome (ARDS)

Infective complications:

- Surgical site infection (superficial)
- Surgical site infection (deep)
- Surgical site infection (organ space)
- Urinary tract infection
- Infection, source uncertain
- Laboratory confirmed blood stream infection

Cardiac complications:

- Myocardial infraction
- o Arrhythmia
- Cardiogenic pulmonary oedema
- o Cardiac arrest with successful resuscitation

Other complications:

- Acute kidney injury
- Pulmonary embolism
- o Stroke
- Acute psychosis or delirium
- o Bowel infarction
- o Anastomotic leak
- Perforation of viscus (e.g. bowel, gall bladder etc.)
- Postoperative haemorrhage
- Other postoperative haemorrhage
- Any other complication

5.8 Plan in case of non-convergence of analysis models

If the statistical models for any of the primary or secondary outcomes do not converge, then the following steps will be taken:

- 1. The model will be fitted without a random intercept for centre
- 2. As above, but excluding any additional covariates apart from minimisation variables
- 3. As above, but also excluding minimisation variables.

5.9 Plan in case of over-stratification

When adjusting for covariates in the primary or secondary analysis models, if there is a category within that covariate where no events have occurred in either of the treatment arms, the statistical model will exclude all patients within this category. To overcome this, this category will be merged with another category; this will be decided by the chief investigator who will be blinded to results. This will apply to the following covariates with three or more categories: (a) Country; (b) Planned surgical procedure. However, if all but one category within that covariate have no events recorded in one of the treatment arms then we will exclude this covariate from the model.

Covariates with only two categories will be excluded from the model if there is a category within that covariate where no events occurred in one of the treatment arms. Covariates with only two categories are: (a) planned use of epidural; (b) Gender (M/F); (c) at least one co-morbid disease (chronic respiratory disease, ischaemic heart disease, diabetes mellitus, heart failure, liver cirrhosis, active cancer, and previous stroke or transient ischaemic attack); (d) smoking status (current smoker); (e) ASA score (I & II vs. III & IV).

5.10 Subgroup analyses

A sub-group analysis will be performed for the primary outcome (composite of pneumonia, endotracheal re-intubation or death within 30 days of randomisation). The subgroup of interest will be planned surgical procedure category. This will comprise the following four groups:

- Lower gastrointestinal (resection of colon, rectum, or small bowel)
- Hepatobiliary (resection of liver, pancreas, or gall bladder)
- Upper gastrointestinal (resection of oesophagus, or resection of stomach (non-obesity surgery))
- Other (obesity surgery, vascular procedure, or other intra-peritoneal surgery)

The sub-group analysis will be performed using the same analysis model as for the primary outcome, except planned surgical procedure will be defined as above, instead of as in the minimisation procedure, and the model will include an interaction term between planned surgical procedure category and treatment arm.

The presence of an interaction will be tested using a Wald test assessing the interaction terms. The test will be considered significant at the 5% level. All patients with complete outcome data will be included in the subgroup analysis. Within each surgical procedure category, we will report summary statistics of the outcome by treatment arm, and a treatment effects and 95% confidence intervals. A p-value for the interaction test will also be reported.

5.11 Per-protocol analysis

A per-protocol analysis using inverse probability-weighting (IPW) [16] will be performed for the primary outcome and the following secondary outcomes: (a) pneumonia within 30 days of randomisation; (b) endotracheal re-intubation within 30 days of randomisation; (c) all-cause mortality within 30 days of randomisation. Participants who are non-adherent will be excluded from the

analysis; non-adherence is defined as (a) a participant in the intervention group who does not receive any CPAP; or (b) a participant in the usual care group who does receive CPAP. As post-randomisation exclusions can cause bias, we will use weighting to account for baseline risk factors that we expect to be joint determinants of adherence and the outcome. We will use the following baseline covariates to calculate weights: age, current smoker, ASA grade, COPD, interstitial lung disease, bronchiectasis, heart failure, liver cirrhosis, active cancer, previous stroke, respiratory infection within the previous month, planned surgical procedure, planned use of epidural, and BMI. Missing data for these baseline covariates will be handled using mean imputation for continuous variables and the missing indicator approach for categorical variables. The probability of non-adherence will be estimated from on a logistic regression model with non-adherence as the outcome, and the covariates mentioned above as fixed terms. Age and BMI will be included as linear terms. The weight is calculated as $\frac{1}{1-P(non-adherenc)}$; weights will be calculated separately in each treatment group. We will then use the same analysis model as for the main analysis, except we will include the Stata options [pw=weight], and vce(robust).

6. Sensitivity Analysis

We anticipate a very small amount of missing data for the primary outcome. If the level of missing data for the primary outcome exceeds 1% of randomised participants, we will perform a sensitivity analysis to assess the robustness of our analysis of the primary outcome data under the assumption that data is missing-not-at-random (MNAR) [2, 17-19]. For example, this could occur if patients who were discharged home and had no postoperative pneumonia were less likely to respond to their telephone follow-up after 30 days, than patients who did have a postoperative pneumonia.

We will perform a sensitivity analysis assuming the data is MNAR based on the following formula:

$$P(Y = 1|X = x) = P(Y = 1|X = x, obs)P(obs|X = x) + P(Y = 1|X, unobs)P(unobs|X = x)$$

Where Y denotes the primary outcome (1=yes, 0=no) and X denotes the treatment allocation (1=treatment, 0=usual care), *obs* denotes that the patient's outcome was available, and *unobs* denotes that the patient's outcome was missing.

In this sensitivity analysis, the odds ratio for the treatment effect will be calculated by:

$$\frac{P(Y = 1|X = 1)/(1 - P(Y = 1|X = 1))}{P(Y = 1|X = 0)/(1 - P(Y = 1|X = 0))}.$$

P(Y = 1 | X = x, obs) will be estimated from the model used in the primary analysis using STATA's 'margins' command. P(obs|X = x) and P(unobs|X = x) will be estimated based on the number of patients with complete and incomplete outcome data in each treatment arm. The probability of an event amongst those with unobserved outcomes in the usual care group, P(Y = 1 | X = usual care, unobs), will be set at 0.05, 0.10 and 0.15. The probability of an event unobserved outcomes amongst those with in the treatment group, P(Y = 1 | X = treatment, unobs), will be set at $P(Y = 1 | X = usual care, unobs) + \delta$. We will use the following values of δ : -0.02, -0.01, 0, +0.01, +0.02.

Confidence intervals will be calculated on the log scale using the standard errors for the log odds ratio from the complete case analysis then transformed to the odds ratio scale.

References

- 1. International Surgical Outcomes Study, g., *Global patient outcomes after elective surgery: prospective cohort study in 27 low-, middle- and high-income countries.* Br J Anaesth, 2016. **117**(5): p. 601-609.
- 2. White, I.R., et al., *Strategy for intention to treat analysis in randomised trials with missing outcome data.* BMJ, 2011. **342**: p. d40.
- 3. Montori, V.M. and G.H. Guyatt, *Intention-to-treat principle.* CMAJ, 2001. **165**(10): p. 1339-41.
- 4. Kahan, B.C., et al., *A re-randomisation design for clinical trials.* BMC Med Res Methodol, 2015. **15**: p. 96.
- 5. Kahan, B.C., et al., *Re-randomization increased recruitment and provided similar treatment estimates as parallel designs in trials of febrile neutropenia.* J Clin Epidemiol, 2018. **97**: p. 14-19.
- 6. Schulz, K.F., et al., CONSORT 2010 statement: updated guidelines for reporting parallel group randomised trials. BMJ, 2010. **340**: p. c332.
- 7. Canet, J., et al., *Prediction of postoperative pulmonary complications in a populationbased surgical cohort.* Anesthesiology, 2010. **113**(6): p. 1338-50.

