3.1 Primary outcome

• Composite endpoint of pneumonia, endotracheal re-intubation or death within 30 days of randomisation.

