4.3 Sample size

The primary outcome is a composite endpoint of pneumonia, re-intubation, or death within 30 days of randomisation. The incidence of postoperative pneumonia in previous trials was 8.0% in the usual care group and 4.3% (relative risk reduction of 46%) in the treatment arm. However, the total number of patients included in these five trials was less than 600 patients. The incidence of postoperative pneumonia, admission to intensive care (a surrogate marker of re-intubation) and death in a large international cohort (n ~9000) was 11.7% for patients aged over 45 years [1]. In order to detect a reduction from 11.7% to 8.8% in the primary outcome measure (relative risk reduction of 25%), with 90% power, a type I error rate of 5%, and a loss to follow up rate of 4%, we would require a total sample size of 4800 patients (2400 per group). This sample size will allow us to detect a 26% relative risk reduction (7.7% vs. 5.7%) in the secondary outcome measure of mortality at one year after randomisation, with 80% power and a type I error rate of 5%. The sample size was calculated, using the *'power two proportions'* function in STATA 14.0 (StataCorp, College Station, USA).

5. Analysis Principles

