5.1 General analysis principles

Analyses will follow the intention-to-treat principle: all randomised patients with a recorded outcome will be included in the analysis, and analysed to the treatment to which they were randomised [2, 3]. Patients will be included in the analysis, regardless of whether the treatment they received was compliant with the protocol. Patients with missing outcome data will be excluded from the analysis. Definitions of what constitutes a recorded outcome for each outcome can be found In Appendix 1. Patients who are re-randomised (i.e. enrolled in PRISM for a repeat surgery despite previous enrolment in PRISM) will be included in the analysis for both randomisations, and treated as independent observations [4, 5].

The magnitude of treatment effect estimate will be reported with 95% confidence interval for primary and secondary outcomes. All p-values will be two-sided, and a significance level of 5% will be used. For each outcome, summary statistics (e.g. mean (SD), number (%)) will be presented separately for each treatment arm.

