5.2.5 Protocol compliance

Numbers and percentages of protocol deviations will be reported. The following protocol deviations will be reported:

- Failure to administer CPAP to a patient in the treatment group
- Starting CPAP at a dose other than 5cmH₂O for a patient in the treatment group
- Administration of CPAP for less than 4 hours duration in the treatment group
- Administration of CPAP with significant interruption for a patient in the treatment group (continuous interruption of more than 15 minutes would usually be considered prolonged).
- Administration of CPAP to a patient in usual care group

We will report the number of patients in each treatment group with at least one of the above protocol deviations. In addition, a separate table as described above will be reported by the method which CPAP was delivered.

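### The per-protocol rule in SAP 5.11 excludes usual care patients for CPAP received at any time, so it can exclude them because of their outcome and bias the odds ratios against CPAP

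*SAP*

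**What the plan says.** Section 5.11 plans an inverse-probability-weighted per-protocol analysis of the primary outcome, pneumonia, re-intubation and 30-day mortality. Non-adherent participants are excluded. In the CPAP arm that means receiving no CPAP at all; in the other arm it means "a participant in the usual care group who does receive CPAP". The section acknowledges that exclusions after randomisation can cause bias and answers this as follows: "we will use weighting to account for baseline risk factors that we expect to be joint determinants of adherence and the outcome". Every listed weighting variable is a baseline one: age, smoking, ASA grade, comorbidities, recent respiratory infection, planned procedure, planned epidural and BMI.

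The compliance list in section 5.2.5 uses the same open wording, "Administration of CPAP to a patient in usual care group", and so do dummy Table 3 and the footnote to Table 18. The only window that the SAP gives for receipt of CPAP, 12 hours from the end of surgery, belongs to the descriptive summary of the CPAP arm (section 5.2.4, Table 11). It is not tied to non-adherence. Section 2.1 describes the intervention as early post-operative CPAP given as routine care. The primary outcome (section 3.1) is "Composite endpoint of pneumonia, endotracheal re-intubation or death within 30 days of randomisation".

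**The concern.** CPAP can be given later to treat pneumonia or respiratory failure. In that case the CPAP follows from the outcome and is not the early routine intervention under test. As worded, the rule still treats it as contamination and removes the patient, and with the patient a usual care event. The rule is one-sided: late CPAP can remove a usual care patient but never a CPAP-arm patient.

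Inverse-probability weights work if adherence is independent of the outcome given the covariates in the weight model. Exclusion triggered by the outcome breaks that condition, whichever baseline covariates are used. The four odds ratios and p-values in Table 18 would be affected. Readers turn to such a table to ask whether non-adherence explains a weak intention-to-treat result, and a bias against CPAP would mislead them on that question.

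**Working it through.** **The plan's own figure.** Section 5.11 states no number, so the design rates come from section 4.3: 11.7% in usual care, 8.8% with CPAP, 90% power, 5% type I error (two-sided, section 5.1) and 4% loss. The standard two-proportion formula without continuity correction gives 2297 per arm, 4594 in total, and 4594 / 0.96 = 4786. That agrees with the stated 4800. With 2400 × 0.96 = 2304 evaluable per arm, power is 90.1%. The design odds ratio is (0.088/0.912) / (0.117/0.883) = 0.728.

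**Effect of the exclusion.** Let c = 0.117 be the usual care risk, f the share of usual care patients with an event who receive CPAP, and g the share of those without an event who do. The SAP gives neither f nor g; both are assumptions.

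- Usual care risk after exclusion = c(1−f) / [c(1−f) + (1−c)(1−g)].
- The usual care odds are multiplied by (1−f)/(1−g), so the odds ratio is multiplied by (1−g)/(1−f).

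With g = 1%:

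| f | Usual care risk analysed | Multiplier | True OR 0.728 becomes | True OR 1.00 becomes |
|---|---|---|---|---|
| 10% | 10.8% | 0.99/0.90 = 1.100 | 0.80 | 1.10 |
| 20% | 9.7% | 0.99/0.80 = 1.238 | 0.90 | 1.24 |
| 30% | 8.6% | 0.99/0.70 = 1.414 | 1.03 | 1.41 |

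With g = 0 the results are 0.81, 0.91 and 1.04 under the design effect, and 1.11, 1.25 and 1.43 under no effect. With g = 2% they are 0.79, 0.89 and 1.02, and 1.09, 1.23 and 1.40. The design effect crosses 1 when (1−g)/(1−f) exceeds 1/0.728. With g = 1% that means f above 1 − 0.99 × 0.728 = 28%.

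The direction depends on f exceeding g. If CPAP went only to patients without events (f = 0, g = 2%), a null odds ratio would move slightly the other way, to 0.98.

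**Can the weights repair it?** A simulation used 400,000 patients, one prognostic baseline covariate, weights 1/(1−P(non-adherence)) fitted within usual care, and a covariate-adjusted outcome model.

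- Exclusion triggered by the outcome, no true effect, f = 10%, 20%, 30%: the unweighted odds ratios were 1.114, 1.258 and 1.434, and the weighted ones were identical. The full-sample value was 1.004.
- The same under the design effect: weighted 0.806, 0.907 and 1.038, against 0.724 in the full sample.
- Exclusion depending on the baseline covariate only: weighted 1.003 to 1.007 against 1.004 under no effect, and 0.722 to 0.724 against 0.724 under the design effect. The unweighted adjusted estimates were equally close here, so this part shows that the definition of non-adherence matters. It does not show that the weights do the work.

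**The case against.** The strongest reply is that the SAP rests on a protocol and case report form that were not part of this check. The usual care rule in 5.11 matches the deviation in 5.2.5, and what counts as that deviation may be limited there to an early period. The context points the same way: the intervention is early CPAP, Table 3 speaks of contamination, and later ventilatory support has its own form page (Appendix 1). This stands as a limit on how often the problem would occur. It does not settle the text. The 12-hour window covers only the CPAP-arm summary, the SAP does not say whether late CPAP would be recorded as non-invasive ventilation, and 5.11 is the operative definition. If a window exists, 5.11 should state it.

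The frequency of outcome-triggered CPAP is also wholly assumed. At f = 10% under no effect, the odds ratio of 1.10 would have an unadjusted 95% interval of about 0.92 to 1.32 with 2304 per arm, and the Table 18 footnotes would show how many patients were excluded. Both points stand and limit the weight of the finding.

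Two further criticisms are tempting but not well supported:

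- A CPAP-arm patient with an event before CPAP could start is also excluded, and a reader might add this to the bias. It pulls the other way, favouring CPAP. Nothing in the SAP allows it to be sized, and it is probably small.
- Country is the one minimisation factor missing from the weight model. The primary outcome model already adjusts for country (5.3), and every model has a random intercept for centre (5.3, 5.4), so this is no separate fault.

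**Conclusion.** The point holds. Followed as written, the usual care rule lets the outcome decide who is excluded, and baseline-only weights leave the resulting bias in place. Provided usual care patients with events receive CPAP more often than those without, the bias runs against CPAP. For f from 10% to 30% with g = 1%, the primary-outcome odds ratio is inflated by a factor of 1.10 to 1.41. The true size cannot be computed from the SAP.

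A reader might infer that the analysis will turn benefit into harm. The figures do not support that: the design effect is attenuated across the range and passes 1 only when about 28% or more of usual care events lead to exclusion. A reader might also infer that the main result is at risk. It is not, because the primary analysis is by intention to treat (5.1) and this analysis is supplementary. The rule should be corrected, but the trial's principal conclusion does not depend on it.

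**What to change.** In section 5.11 and the matching Table 18 footnote, count CPAP in a usual care participant as non-adherence only if it started within the window that the protocol sets for study CPAP and before any component of the primary outcome. CPAP started later, or after an event, would not exclude the participant. State the window in 5.11 even if the protocol already has it.

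Add a rule, fixed in advance and applied blind to allocation and results as far as the data allow, for participants whose timing is unclear. This is needed because Appendix 1 derives the outcomes from dates, not clock times, and the SAP shows no CPAP start time for usual care patients, so same-day CPAP and events may not be separable.

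For the CPAP arm, a sentence noting that a very early event can prevent CPAP from starting, with the number of such patients, is enough.

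The cost is a change of wording and code, plus a few participants with ambiguous timing. Sample size and the primary analysis do not change. CPAP given inside the window to a patient already deteriorating would still count as non-adherence, so the result should still be read as supplementary.

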4.2 Randomisation

Randomisation will occur after the participant has provided informed consent and up to four hours after the end of surgery. Participants will be centrally allocated to treatment groups (1:1) by a computer-generated dynamic procedure (minimisation) with a random component. Minimisation variables will be country, surgical procedure category and planned use of epidural anaesthesia. The surgical procedure categories are as follows: (a) resection of colon, rectum or small bowel; (b) resection of liver, pancreas or gall bladder; (c) resection of stomach (non-obesity surgery); (d) resection of oesophagus (non-obesity surgery); (e) obesity surgery; (f) vascular procedure; or (g) other intra-peritoneal surgery. Each participant will be allocated with 80% probability to the group that minimises between group differences in these factors among all participants recruited to the trial to date, and to the alternative group with 20% probability. To enter a patient into the PRISM trial, research staff at the site will log on to a secure web-based randomisation and data entry platform and complete the patient's details to obtain a unique patient identification number and allocation to a treatment group.

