5.2.3 Clinical management

Clinical management for the treatment group and usual care group will be summarised but not subjected to statistical testing. Numbers (%) and means (SD) or medians (IQR) will be provided separately for each group. The treatment and usual care groups will be compared for the following clinical management characteristics:

- Surgery: open surgical technique; anaesthetic technique; mechanical ventilation during surgery
- Intravenous fluids during surgery: total intravenous fluid administered excluding blood products; total volume of blood products administered
- Planned and actual level of care on the first night after surgery
- Respiratory support after surgery within four hours of the end of surgery

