Median (IQR)				 	
^a Maximum set tidal volume (ml)				1	
Mean (SD)				1	
Median (IQR)					
^a Maximum respiratory rate (min ⁻¹)					
Mean (SD)				-	
Median (JQR)					
^a Maximum FiO ₂ (%)					
Mean (SD)					
Median (JQR)				+	
Intravenous fluids during surgery				+	
Total volume of intravenous fluid administered excluding blood products (mL)					
Mean (SD)				-	
Median (JQR)				-	
Total volume of blood products administered (mL)				-	
Mean (SD)					
Median (IQR)				+	
Planned level of care on the first night after surgery - no. (%)					
Critical care unit level 3					
Critical care unit level 2					
Post- anaesthesia care unit					
Surgical ward				───	
Level of care on the first night after surgery - no. (%)				───	
Critical care unit level 3				 	
Critical care unit level 2				 	
Post- anaesthesia care unit				 	
Surgical ward				 	
Respiratory support after surgery (within 4 hours of the end of surgery) - no. (%)				 	
Invasive mechanical ventilation				 	
Non-invasive mechanical ventilation				 	
High flow nasal oxygen therapy Abbreviation: SD, standard deviation; IQR, Interguartile range					

Abbreviation: SD, standard deviation; IQR, Interquartile range

^a Only summarised for patients who received mechanical ventilation during surgery

Table 3: Adherence and contamination

Adherence and contamination - no. (%)	Usual Care (n=XXXX)	CPAP (n=XXXX)
Patients with ≥ 1 treatment deviation	XX (XX.X %)	XX (XX.X %)
Total number of deviations	XXX	XXX
Number of treatment deviations per patient		
0	XXX (XX.X %)	XXX (XX.X %)
1	XXX (XX.X %)	XXX (XX.X %)
2	N/A	XXX (XX.X %)
3	N/A	XXX (XX.X %)
Types of deviations		
Participant in the intervention group did not receive CPAP	N/A	XXX (XX.X %)
CPAP administered for less than 4 hours duration	N/A	XXX (XX.X %)
CPAP administered with significant interruption	N/A	XXX (XX.X %)
CPAP started at a dose other than 5 cmH ₂ O	N/A	XXX (XX.X %)
Participant in the usual care group did receive CPAP	XXX (XX.X %)	N/A

Table 4: Adherence and contamination by CPAP delivery method

		CPAP ^a (n=XXXX)					
Adherence and contamination - no. (%)	Face mask (n=XXXX)	Helmet device (n=XXXX)	Nasal mask (n=XXXX)				
Patients with ≥ 1 treatment deviation	XX (XX.X %)	XX (XX.X %)	XX (XX.X %)				
Total number of deviations	XXX	XXX	XXX				
Number of treatment deviations per patient							
0	XXX (XX.X %)	XXX (XX.X %)	XXX (XX.X %)				
1	XXX (XX.X %)	XXX (XX.X %)	XXX (XX.X %)				

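### The per-protocol weights leave out planned level of care on the first night, a collected variable that plausibly affects both CPAP receipt and risk, so some confounding may remain

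*SAP*

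**What the plan says.** Section 5.11 excludes non-adherent participants. In the CPAP arm that means "a participant in the intervention group who does not receive any CPAP"; in the usual care arm it means anyone who did receive CPAP. The section recognises that such exclusions can bias the comparison and states the purpose of the weights: "we will use weighting to account for baseline risk factors that we expect to be joint determinants of adherence and the outcome". The covariate list opens with "We will use the following baseline covariates to calculate weights: age, current smoker, ASA grade, COPD, interstitial lung disease, bronchiectasis" and ends with "planned surgical procedure, planned use of epidural, and BMI". In between stand heart failure, liver cirrhosis, active cancer, previous stroke and recent respiratory infection. On estimation, "weights will be calculated separately in each treatment group". The weighted analysis then reuses the main outcome models with robust variance.

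Those models are:

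- **Primary composite (5.3):** random centre intercept, country, epidural, procedure, age, gender, any comorbidity, smoking and ASA.
- **Pneumonia, re-intubation and 30-day death (5.4):** random centre intercept, epidural and procedure only.

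Section 5.2.3 lists "Planned and actual level of care on the first night after surgery" among the clinical management items. Appendix 2, Table 2 has a separate block headed "Planned level of care on the first night after surgery - no", with four categories: level 3, level 2, post-anaesthesia care unit and surgical ward.

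**The concern.** Non-adherence in the CPAP arm means receiving no CPAP at all. Whether the planned destination has the staff and equipment to deliver CPAP is a natural determinant of that. The planned destination also tends to reflect how much risk the clinical team sees in the patient. A variable of this kind is what 5.11 says the weights are for. Every covariate on the list describes the patient or the operation; none describes the care setting.

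Suppose CPAP is missed more often in patients planned for a ward. Dropping them leaves a CPAP group with too many higher-risk patients, and the per-protocol odds ratio moves towards harm. Suppose usual-care patients in critical care more often receive CPAP. Dropping them leaves a lower-risk usual care group and pushes the same way. With the opposite patterns the bias reverses. Four odds ratios with p-values are to be reported from this analysis (Table 18).

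**Working it through.** **1. Where the variable appears.**

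| Place in the SAP | Planned level of care |
|---|---|
| 5.2.3 and Table 2 | collected, separately from actual level |
| 5.2.2 baseline characteristics | not listed |
| 5.11 weight model | not listed |
| 5.3 model (primary outcome) | not listed |
| 5.4 model (three secondary outcomes) | not listed |

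**2. A yardstick for size.** The point turns on no figure in the SAP, but the sample size (4.3) gives a scale. With 11.7% vs 8.8%, two-sided 5% and 90% power:

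n = [1.960·√(2·0.1025·0.8975) + 1.282·√(0.117·0.883 + 0.088·0.912)]² / 0.029² = 2297 per group.

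Dividing by (1 − 0.04) gives 2393, or 4786 in total, against the stated 4800. The figure reproduces.

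With 2400 × 0.96 = 2304 evaluable per arm:

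SE(log OR) = √[1/(2304·0.117) + 1/(2304·0.883) + 1/(2304·0.088) + 1/(2304·0.912)] ≈ 0.098.

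The 95% interval therefore extends by a factor of exp(1.96 × 0.098) ≈ 1.21 each way.

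**3. Bias when only the CPAP arm deviates.** All inputs are assumed. There is no true effect. A share q is planned for critical care, with event risks rc (critical care) and rw (ward) and CPAP non-receipt nc and nw.

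- Adherent CPAP-arm risk = [q(1−nc)rc + (1−q)(1−nw)rw] / [q(1−nc) + (1−q)(1−nw)]
- Usual care risk = q·rc + (1−q)·rw

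Example with q = 0.5, risks 14% and 7%, non-receipt 5% and 20%: the CPAP-arm risk is (0.5·0.95·0.14 + 0.5·0.80·0.07)/(0.475 + 0.400) = 0.1080, against 0.1050. The odds ratio is 1.032 instead of 1.000.

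Over q = 0.3, 0.5, 0.7 and risks 14% vs 7% or 12% vs 8%:

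| Non-receipt, critical care vs ward | Overall non-receipt | Odds ratio (truth 1.00) |
|---|---|---|
| 2% vs 8% | about 4–6% | 1.005–1.012 |
| 5% vs 20% | 9.5–15.5% | 1.01–1.03 |
| 3% vs 30% | 11–22% | 1.03–1.06 |
| 20% vs 5% (reversed) | 9.5–15.5% | 0.97–0.985 |

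**4. Bias when both arms deviate**, which is the contrast 5.11 plans. Also assumed: no true effect; 40% planned for higher-level care; overall risk 11.7%; outcome odds ratio for the setting 1.5 to 3; non-adherence risk ratio (higher-level care vs other) 1/2 to 1/3 in the CPAP arm and 2 to 3 in usual care; setting unrelated to the covariates already used.

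| Non-adherence, CPAP / usual care | Factor on the odds ratio |
|---|---|
| 5% / 1% | 1.004–1.016 |
| 10% / 3% | 1.009–1.037 |
| 20% / 5% | 1.019–1.078 |

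If setting is unrelated to adherence, or unrelated to outcome, the factor is 1.000.

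**5. Against the yardstick.** ln(1.03)/0.098 ≈ 0.3 standard errors; ln(1.06)/0.098 ≈ 0.6; ln(1.078)/0.098 ≈ 0.8.

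**The case against.** The strongest reply is that 5.11 confines the weights to baseline factors, and the SAP does not treat planned level of care as one. It is filed under clinical management and is absent from 5.2.2. Allocation is open, and on timing the SAP says: "Randomisation will occur after the participant has provided informed consent and up to four hours after the end of surgery". It never says when the plan was recorded. A reader might take it to be pre-operative, but that is an inference. If it was recorded after allocation, it does not belong in the weights. This stands, and it is why the fix is conditional.

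The authors also pre-specified 14 covariates on subject-matter grounds, and nothing in the SAP links planned level of care to CPAP receipt or risk. A reader might conclude that the per-protocol estimates are confounded. The document does not support that: the link is plausible but undocumented. ASA grade, procedure, epidural and the centre intercept (with country as well for the primary outcome) may absorb part of it. Equally, the SAP gives no reason for leaving the variable out.

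Two further readings go too far. Usual care is not an unselected comparator, because its CPAP recipients are excluded too; step 3 of the working is therefore only the special case without such exclusions. Sex, asthma, ischaemic heart disease and diabetes are also outside the weight list, but nothing in the SAP suggests that they determine CPAP receipt. For the primary outcome, the gender and any-comorbidity terms largely cover them.

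Finally, the stakes are low. Since any CPAP counts as adherent in the CPAP arm, non-adherence may be small, and then so is the bias.

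**Conclusion.** The point holds as a minor one. Planned level of care is a collected candidate joint determinant that is in neither the weights nor the reused outcome models, so some confounding may remain in the four per-protocol odds ratios. Before adjustment, the plausible size is a factor of about 1.00 to 1.03 with modest non-adherence (1.037 in the most extreme cell at 10% and 3%). It reaches about 1.06 to 1.08 only where non-adherence is heavy and strongly tied to setting in one or both arms. The direction reverses if CPAP is missed mainly in critical care. Even the largest value is under one standard error of the log odds ratio. All of this rests on assumed adherence rates, risk differences and setting shares. Adjustment already in the plan should reduce it. The intention-to-treat analysis is unaffected and no figure in the SAP changes.

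**What to change.** In 5.11, add planned (not actual) level of care on the first night, as a categorical term with the Table 2 categories, to the weight model in each arm, provided it was recorded before randomisation. State when it was recorded. If the timing is uncertain, report the per-protocol results with and without the term. Settle this before outcome data are inspected, in line with section 2.2.

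The cost is one or two sentences and three more indicator terms per arm in an existing model, using data already collected. The downside is slightly more variable weights.
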